### **6.13.5. Vital Signs and Other Physical Findings**

Analyses will be conducted on vital signs and physical characteristics including systolic blood pressure (mmHg), diastolic blood pressure (mmHg), pulse (bpm), weight (kg) and BMI (kg/m^2).

Treatment group comparisons will be conducted for Safety Population for Period 2 using an ANCOVA model with treatment group and baseline value for continuous data and Fisher's exact test for categorical data as described in Section 6.1.2.1. Only categorical safety data will be summarized for the IR Population.

Change from baseline to last observation for vital signs and physical characteristics will be summarized for patients who have both baseline and at least 1 postbaseline result, for Periods 2, respectively:

- The scheduled visits/measurements will be included. The unscheduled visits and the repeat measurements will be excluded.
- Data will be analyzed based on original scale.

For vital signs and physical characteristics, the observed values at each visit (starting at baseline) and change from baseline to each scheduled visit, respectively, will be displayed in box plots for patients who have both a baseline and at least one postbaseline result. These box plots will be used to evaluate trends over time and to assess a potential impact of outliers on central tendency summaries.

- The scheduled visits/measurements will be included. The unscheduled visits and the repeat measurements will be excluded.

- The following summary statistics will be included as a table below the box plot: number of patients with a baseline and at least 1 postbaseline result, mean, SD, minimum, Q1, median, Q3, and maximum.
- Data will be summarized based on original scale.

To assess the effect of administration of study drug on vital signs (blood pressures and pulse rate) among patients, at Week 0 and any visit where biologic rescue of ixekizumab 80 mg Q2W was initiated, vital signs will be measured before the first injection and approximately 1 hour after the injection. The box plots will be produced for pre-dose and post-dose vital signs at Week 0 (Visit 2), Week 16 (Visit 8), and any visits after for patients who have pre- and post-dose vital signs.

The number and percentage of patients with treatment-emergent or follow-up emergent high or low vital sign and weight at any time for Periods 2 and 3, respectively, will be summarized. The comparisons between and among treatment groups will be conducted using Fisher's exact test for the Safety Population for Period 2.

- [Table RHBX.6.9](#) defines the high and low baseline values as well as the limits that are specified as treatment-emergent and follow-up emergent. Note that weight does not have an abnormal baseline; therefore, the treatment-emergent and follow-up emergent values are determined by change from baseline.
- All postbaseline scheduled, unscheduled, and repeated measurements will be included.
- To assess increases, change from the maximum value during the baseline period or baseline to the maximum value during each study period will be used.
- To assess decreases, change from the minimum value during the baseline period or baseline to the minimum value during each study period will be used.
- For treatment-emergent high and low:
  - A treatment-emergent **high** result is defined as a change from a value less than or equal to the high limit at baseline to a value greater than the high limit at any time that meets the specified change criteria during the treatment period.
  - A treatment-emergent **low** result is defined as a change from a value greater than or equal to the low limit at baseline to a value less than the low limit at any time that meets the specified change criteria during the treatment period.
- For follow-up emergent high and low:
  - A follow-up emergent **high** result is defined as a change from a value less than or equal to the high limit at baseline to a value greater than the high limit at any time that meets the specified change criteria during the follow-up period.
  - A follow-up emergent **low** result is defined as a change from a value greater than or equal to the low limit at baseline to a value less than the low limit at any time that meets the specified change criteria during the follow-up period.

**Table RHBX.6.9. Categorical Criteria for Abnormal Treatment-Emergent Blood Pressures and Pulse Measurement, and Categorical Criteria for Weight Changes for Adults**

Parameter	Low	High
Systolic BP (mm Hg) a (supine or sitting – forearm at heart level)	≤90 and decrease from baseline ≥20	≥140 and increase from baseline ≥20
Diastolic BP (mm Hg) a (supine or sitting – forearm at heart level)	≤50 and decrease from baseline ≥10	≥90 and increase from baseline ≥10
Pulse (bpm) a (supine or sitting)	<50 and decrease from baseline ≥15	>100 and increase from baseline ≥15
Weight (kg)	(Loss) decrease from baseline ≥7%	(Gain) increase from baseline ≥7%

Abbreviations: BP = blood pressure; bpm = beats per minute; kg = kilogram; mm Hg = millimeters of mercury.

a Baseline abnormal values are defined by the value presented.

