#### **8.2.2. Adverse Events of Special Interest**

The following adverse events of special interest (AESIs) will be used to determine the safety and tolerability of ixekizumab over the range of doses selected for this clinical study.

AESIs for ixekizumab are:

- cytopenias (leukopenia, neutropenia, and thrombocytopenia)
- clinically significant hepatic events and/or significant elevations in liver function test changes/enzyme elevations (ALT, AST, bilirubin, and alkaline phosphatase)
- infections
- injection-site reactions
- allergic reactions/hypersensitivities
- cerebrocardiovascular events
- malignancies
- IBD

- depression.

Sites will provide details on some of these AEs as instructed on the CRF. Investigators will also educate patients and/or caregivers about the symptoms of allergic/hypersensitivity reactions and will provide instructions on dealing with these reactions (see also Section 6.6.1). A blood sample will be collected as soon as possible for any patient who experiences an AE of a potential systemic allergic /hypersensitivity reaction during the study as judged by the investigator.

Data on preferred terms associated with cerebrocardiovascular events (defined as death, cardiac ischemic events including MI and hospitalization for unstable angina, hospitalization for heart failure, serious arrhythmia, resuscitated sudden death, cardiogenic shock, coronary revascularization procedure, stroke/transient ischemic attack, peripheral revascularization procedure, peripheral arterial event, and hospitalization for hypertension) will be collected, and these events and any deaths will be adjudicated by an external clinical events committee (CEC) made up of a chairman, 2 cardiologists, and a neurologist.

Data on suspected IBD, as identified by events possibly indicative of ulcerative colitis and Crohn's disease, will be collected and the events will be adjudicated by an external CEC with expertise in IBD.

The role of external CECs is to adjudicate defined clinical events in a blinded, consistent, and unbiased manner throughout the course of a study. The purpose of the CEC for adjudication of cerebrocardiovascular events and the CEC for adjudication of suspected IBD events is to ensure that all reported events are evaluated uniformly by a single group.

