**Illustration of study design for Clinical Protocol I1F-MC-RHBX (footnotes)**

- a All patients will receive 2 injections at baseline at Week 0 to maintain the blind with a 80-mg or 160-mg starting dose of ixekizumab or placebo.
- b Beginning at Week 16 and up to Week 44, any patient, regardless of their original treatment group, may be identified by an investigator based on clinical judgment as an inadequate responder and receive rescue treatment. At such time changes in background therapy (including, but not limited to NSAIDs, nonbiologic DMARDs or the use of rescue biologic treatment) can be made at the discretion of the investigator, while remaining blinded to the original randomization treatment assignment. Changes in ongoing medications at that time can include changes in dose of NSAIDs or nonbiologic DMARDs, including the introduction of new medications. Investigator may also decide to use biologic rescue of ixekizumab 80 mg Q2W with an 80-mg starting dose.
- c Following any treatment modifications, investigators are to reevaluate the clinical status of the patient as appropriate to assess effect of treatment modification. Treatment guidelines recommend a minimum period of 12 weeks to evaluate effect of biologic treatment modifications; however, if in the opinion of the investigator, a patient does not show any clinical improvement after at least 8 weeks of the ixekizumab 80 mg Q2W treatment modification, then the investigator may consider discontinuation of the patient from ixekizumab treatment. Such patients may then receive other medical therapies (potentially including a TNF inhibitor) that are prescribed by their physician and are to remain in the study until Week 52 per study schedule.
- d Patients who have taken at least 1 study dose and who discontinue study treatment prior to Week 16 or study participation (regardless of timing) are to complete an ETV and enter into post-study follow-up for at least 12 weeks after the ETV date or the last regularly scheduled visit. Patients whose ETV or last regularly scheduled visit is longer than 12 weeks after their last investigational study medication dose are not required to enter into the Post-Study Follow-Up Period. V801 and V802 are required for patients in the Post-Study Follow-Up Period; V803 may be needed depending on neutrophil counts.

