**Safety Population:** Safety analyses for Period 2 will be conducted on the Safety Population, defined as all randomized patients who received at least 1 dose of study treatment. For patients who were deemed as inadequate responders by their investigators and were treated with biologic rescue of ixekizumab 80 mg Q2W, only data up to the time of initiation of biologic rescue of ixekizumab 80 mg Q2W will be included in the Period 2 analyses. Patients will be analyzed according to the treatment to which they were assigned at Week 0.

**Inadequate Responder (IR) Population:** Selected safety and efficacy summaries will be provided for the IR Population, defined as inadequate responders (identified by investigators based on clinical judgment) who had initiated biologic rescue of ixekizumab 80 mg Q2W.

**Follow-Up Population:** Safety analyses for Period 3 will be conducted on the Follow-Up Population, defined as all randomized patients who received at least 1 dose of study treatment and have entered the Period 3. Patients will be analyzed according to the treatment they received before entering the Follow-up Period.

[Table RHBX.6.1](#) summarizes the major analysis purposes intended for each analysis population.

[Table RHBX.6.2](#) describes the treatment groups and the comparisons for each study period and analysis population.

Table RHBX.6.1. Major Analysis Purposes Intended for Each Analysis Population

	Intent-to-Treat (ITT) Population	Per-Protocol Set (PPS)	Inadequate Responder (IR) Population	Safety Population	Follow-Up Population
Disposition	x		x		x
Baseline Characteristics a	x		x		
Treatment Compliance			x	x	
Concomitant Medication	x		x b		
Protocol Deviation	x		x b		
Exposure			x b	x	
Efficacy and Health Outcomes Analyses	x	For ASAS40	Selected efficacy b		
Safety Analyses			Categorical safety b	x	x
Subgroup Analyses on Efficacy	x				
Subgroup Analyses on Safety Outcome				x	

Abbreviation: ASAS40 = Assessment of Spondyloarthritis International Society 40.

a Including patient demographics and other baseline characteristics, historical illness, preexisting conditions, prespecified medical history, previous therapy.

b These summaries will focus on the time period during biologic rescue of ixekizumab 80 mg every 2 weeks (Q2W).

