#### **6.13.3.1. Special Safety Topics including Adverse Events of Special Interest**

Safety information on special topics including AEs of special interest (AESIs) will be presented by treatment group for the Safety Population in Period 2. Selected AESIs (ie, Hepatic, Allergic Reactions/Hypersensitivities, Injection Site Reactions, and Inflammatory Bowel Disease [IBD]) will also be summarized by treatment group for the Safety Population in the period between Week 0 and Week 16. In addition, summaries for TEAEs for AESIs will be provided for the IR Population during biologic rescue including ixekizumab 80 mg Q2W. No separate summaries for SAEs or AEs leading to discontinuation for AESIs will be provided for these patients since the incidences of these events are expected to be low and they will be summarized in the overall SAEs and AEs leading to discontinuation reports for the IR Population.

Exposure-adjusted incidence rates will also be summarized for selected AESIs (ie, Hepatic, Allergic Reactions/Hypersensitivities, Injection Site Reactions, and IBD) for the Safety Population in Period 2, and for IR population.

[Table RHBX.6.8](#) provides the definitions/derivations and analyses methods (including analyses, summaries and by-patient listings) of special safety topics including AESIs.

Potential AESIs will be identified by a Standardized MedDRA Query (SMQ) or a Lilly-defined MedDRA PT listing. Preferred terms within an SMQ will be classified as broad and narrow. In the Lilly-defined MedDRA PT listings, Lilly has provided the broad and narrow classification. The Lilly-defined broad terms are for a more sensitive search of potential events of interest and the Lilly-defined narrow terms are for a more specific search. Therefore, the summaries will include the classifications of broad term (same as pooling narrow and broad terms together) and narrow term.

In the event that the listing of terms or analysis changes for a special safety topic, it will be documented in the program safety analysis plan (PSAP) which will supersede this document; it will not warrant an amendment to the individual study SAP.

Fisher's exact tests will be used to compare the treatment group for the Safety Population during Period 2 and during period between Week 0 and Week 16.

In general, an AESI summary will not be provided for Follow-Up Population during Period 3 except for hepatic laboratory tests.

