The QIDS-SR16 total score is the sum of the above domain scores. The total score will be missing if any domain score is missing.

The QIDS-SR16 total scores are categorized as follows:

- None (no depression): 0 – 5
- Mild: 6 – 10
- Moderate: 11 – 15
- Severe: 16 – 20
- Very severe: 21 – 27.

The following summaries will be produced for QIDS-SR16 total score category by treatment groups for the Safety Population during the Period 2:

- The number and percentage of patients falling into each QIDS-SR16 total score category at each scheduled visit.
- Shift from maximum baseline to each postbaseline visit in QIDS-SR16 total score category.
- The number and percentage of patients falling into the following categories based upon the maximum postbaseline QIDS-SR16 total score:
  - Improved; maximum postbaseline category < maximum baseline category.
  - Worsened; maximum postbaseline category > maximum baseline category.
  - Same; maximum postbaseline category = maximum baseline category.

In addition, the number and percentage of patients falling into the following groups based upon the maximum postbaseline QIDS-SR16 item 12 (Thoughts of Death or Suicide) score will be summarized by treatment groups for Safety Population during Period 2:

- Improved; maximum postbaseline QIDS-SR16 item 12 score < maximum baseline item 12 score.
- Worsened; maximum postbaseline QIDS-SR16 item 12 score > maximum baseline item 12 score.
- Same; maximum postbaseline QIDS-SR16 item 12 score = maximum baseline item 12 score.

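### High/low vital signs and weight are tested on crude Period 2 percentages although follow-up stops at rescue; four grouped AESI tables and the worst-score QIDS categories have a narrower version of the same gap

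*SAP*

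**What the plan says.** **Follow-up.** For rescued patients in the Safety Population, SAP 6.1.1 states that "only data up to the time of initiation of biologic rescue of ixekizumab 80 mg Q2W will be included in the Period 2 analyses". The study design footnotes set the rescue window: "Beginning at Week 16 and up to Week 44, any patient, regardless of their original treatment group, may be identified by an investigator" as an inadequate responder.

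**Vital signs and weight.** SAP 6.13.5 counts "The number and percentage of patients with treatment-emergent or follow-up emergent high or low vital sign and weight at any time for Periods 2", with Period 3 alongside. It uses the period maximum to assess increases and the period minimum to assess decreases, and names Fisher's exact test for Period 2. No Week 0-16 or exposure-adjusted version is given. By visit, "the observed values at each visit (starting at baseline) and change from baseline to each scheduled visit, respectively, will be displayed in box plots", with summary statistics below the plots. The continuous comparison is change to last observation.

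**Laboratory tests.** SAP 6.13.4 and 6.13.4.1 analyse categorical abnormalities both for Period 2 and for Week 0-16.

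**AESIs.** Protocol 8.2.2, under "AESIs for ixekizumab are", lists nine. In SAP 6.13.3.1, "Selected AESIs (ie, Hepatic, Allergic Reactions/Hypersensitivities, Injection Site Reactions, and Inflammatory Bowel Disease [IBD]) will also be summarized by treatment group" for Week 0-16, and "Exposure-adjusted incidence rates will also be summarized for selected AESIs", naming the same four. Table RHBX.6.8 specifies Fisher's exact test for the grouped cytopenia, cerebro-cardiovascular, malignancy and depression tables.

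**QIDS-SR16.** SAP 6.13.6 plans "The number and percentage of patients falling into the following categories based upon the maximum postbaseline QIDS-SR16 total score" for Period 2, and does the same for Item 12. It names no test. It also gives the total-score category, and the shift from maximum baseline, at each scheduled visit.

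**The concern.** An outcome counted if it ever occurs, or read from the worst value, becomes more likely as observation lengthens. The Schedule of Activities has 13 postbaseline blood pressure and pulse visits through Week 52, six of them by Week 16 (Weeks 1, 2, 4, 8, 12 and 16). A patient rescued at Week 16 contributes at most those six; an unrescued completer contributes all 13. Weight is entered on the eCRF after baseline only at Weeks 16, 24 and 52 and at early termination, so the same patient contributes one scheduled weight instead of three.

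Rescue follows a judgement of inadequate response, and the sample-size section assumes Week 16 ASAS40 rates of 46% on ixekizumab Q2W and 18% on placebo. More rescue on placebo is therefore plausible. That would make blood pressure, pulse and weight abnormalities look commoner on ixekizumab for a reason unrelated to the drug. Imbalance the other way could mask a real excess.

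**Working it through.** **1. Which outcomes have a second version that deals with unequal follow-up?**

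| Outcome | Week 0-16 | Exposure-adjusted |
|---|---|---|
| TEAEs by severity, SOC and PT; overall AE summary, including AESIs | Yes (6.13.2) | Yes (6.13.2) |
| SAEs; AEs leading to discontinuation | Yes (6.13.3) | Yes (6.13.3) |
| Categorical laboratory tests | Yes (6.13.4) | No |
| Hepatic, allergic, injection-site and IBD events | Yes (6.13.3.1) | Yes (6.13.3.1) |
| Infections (the whole SOC) | Through the SOC tables | Through the SOC tables |
| Cytopenia TEAEs, grouped | No (laboratory shifts only) | No |
| Malignancies, depression, adjudicated cerebro-cardiovascular events, grouped | No | No |
| High/low vital signs and weight | No | No |
| QIDS total-score category by visit | Week 16 row | No |
| Worst-score QIDS total and Item 12 | No | No |

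Nine AESIs minus four leaves five without dedicated second tables. Infections are covered at SOC level, so four grouped tables remain.

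**2. How large could the bias be?** The plan states no figure to reproduce, so this is an illustration. Assumptions: the same constant hazard in both arms, no drug effect, rescue times uniform over Weeks 16-44, and no other dropout. The 52-week risk p and the rescue proportion r are assumed.

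- Hazard per week: h = -ln(1 - p)/52.
- Mean risk before rescue in rescued patients: q = 1 - [exp(-16h) - exp(-44h)]/(28h).
- Expected crude percentage: (1 - r)p + rq.
- Mean follow-up in weeks: 52(1 - r) + 30r.

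For p = 10%, h = 0.002026 and q = 5.885%. For p = 20%, h = 0.004291 and q = 12.027%. Worked example, p = 10%: at r = 60%, 0.4 x 10 + 0.6 x 5.885 = 7.53%; at r = 30%, 0.7 x 10 + 0.3 x 5.885 = 8.77%.

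| p | Rescue, placebo v ixekizumab | Mean follow-up (weeks) | Crude %, placebo v ixekizumab | Ratio, ixekizumab/placebo |
|---|---|---|---|---|
| 10% | 60% v 40% | 38.8 v 43.2 | 7.53 v 8.35 | 1.11 |
| 10% | 60% v 30% | 38.8 v 45.4 | 7.53 v 8.77 | 1.16 |
| 20% | 60% v 40% | 38.8 v 43.2 | 15.22 v 16.81 | 1.10 |
| 20% | 60% v 30% | 38.8 v 45.4 | 15.22 v 17.61 | 1.16 |
| 10% or 20% | 40% v 40% | 43.2 v 43.2 | equal | 1.00 |

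Reversing 60% v 40% gives 0.90; reversing 60% v 30% gives 0.86.

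**3. Do the existing tools remove it?** A Week 0-16 table gives the same expected percentage in both arms (3.19% at p = 10%, 6.64% at p = 20%). The SAP's exposure-adjusted rate divides patients with an event by total exposure. For p = 10% and 60% v 30%, that ratio is (8.77/45.4)/(7.53/38.8), about 0.99; over the four unequal-rescue rows above it lies between 0.99 and 1.00.

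**4. Effect on the test.** With 100 patients per arm, exact enumeration puts the chance of p <= 0.05 with no drug effect at 2.8% for p = 10% and equal 40% rescue, and 3.5% for 60% v 30%. At p = 20% the figures are 3.3% and 5.2%. The main damage is to the estimate; false positive tests become only slightly more frequent.

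**The case against.** The other side has four good arguments.

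- **Much is already covered.** A reader might infer that five of the nine AESIs, and mood as a whole, rest only on crude Period 2 percentages. The documents do not support that. The infection AESI is the whole Infections and infestations SOC, which has SOC-level TEAE tables in both forms. Cytopenias have Week 0-16 laboratory shifts. QIDS is scheduled after baseline only at Weeks 16, 36 and 52 and at early termination, so the Week 16 rows of the by-visit tables are close to an equal-follow-up analysis of the total score. Table RHBX.6.7 adds by-visit ANCOVA for the nine domains and Item 12. The overall AE summary, which includes AESIs, appears in both forms. This stands and limits the point.
- **Individual terms are visible.** PTs for depression and malignancy appear in the general Week 0-16 and exposure-adjusted tables, and vital-sign findings that lead to a diagnosis are reported as AEs. This stands in part. Scattered PTs do not rebuild an SMQ group or an adjudicated category, and a threshold crossing without a diagnosis is not an AE.
- **Week 0-16 loses information.** Making it the only between-arm test would discard late events and leave one scheduled postbaseline weight. This stands, so the fix adds analyses and removes none.
- **Rescue rates are unknown.** This stands. Neither size nor direction can be fixed from the documents. The revision history lists the added Week 0-16 and exposure-adjusted analyses without a reason, so one cannot say that the SAP acknowledges this bias.

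The vital-sign box plots do not answer the point: no between-arm test is stated for them, and after Week 16 they show only unrescued patients.

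**Conclusion.** The point holds in a limited form. It is firmest for high/low vital signs and weight: the only between-arm test of these categories uses crude Period 2 percentages cut at rescue, while laboratory abnormalities of the same structure also get a Week 0-16 test. It holds to a lesser degree for the grouped malignancy, depression, adjudicated cerebro-cardiovascular and cytopenia TEAE tables. For worst-score QIDS total and Item 12 it is a labelling matter, since 6.13.6 names no test and only the SAP's general Fisher rule for categorical safety data would apply.

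Under the assumed rescue patterns the spurious ratio is about 1.10 to 1.16. Earlier rescue would enlarge it, equal rescue would remove it, and more rescue on ixekizumab would reverse it. The constant hazard is only a rough description of weight and QIDS, which are measured at few visits. A reader might infer that ixekizumab will necessarily look worse; without rescue rates the documents do not support that. These are safety tables outside the multiplicity scheme, so efficacy conclusions are unaffected.

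**What to change.** 1. In SAP 6.13.5, add the Week 0-16 categorical analysis already used for laboratory tests to high/low blood pressure, pulse and weight. Note that Week 16 is the only scheduled postbaseline weight recorded in that window.
2. In SAP 6.13.3.1 and Table RHBX.6.8, extend the planned exposure-adjusted rates to the grouped malignancy, depression, adjudicated cerebro-cardiovascular and cytopenia TEAEs, with Week 0-16 tables as support.
3. Keep the crude Period 2 tables, including the worst-score QIDS total and Item 12 categories. Add a footnote that follow-up is truncated at rescue and may differ by arm, and show mean pre-rescue exposure by arm.

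Infections and the by-visit QIDS total-score category need no change. Week 0-16 should not become the only between-arm test.

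The cost is some SAP wording and reruns of existing table programs; no new data are needed. The downside is a few more tables, and few events in the Week 0-16 window.
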